### **I. Provisions to Monitor the Data to Ensure the Safety of Subjects**

Data will be maintained on the Prisma Health REDCap and a secure server with password protection. Study data and signed consent documents will be stored in a locked office in Prisma Health Orthopedics. Only authorized research members of this study can access this information. The researchers involved in this study commit to handle all information with care and to protect research subjects' identities.

## **7) Risks to Subjects**

Potential risks to subjects include adverse reactions to the oral immunonutrition supplementation:

#### Omega-3 fatty acids (LOVAZA), 1.68 grams/day:

The FDA states that  $\leq 3.0$  grams/day of EPA + DHA is safe for humans. The daily supplementation provided to patients per this protocol is 1.68 grams/day (0.93 grams/day EPA + 0.75 grams/day DHA), well below the tolerable threshold.

Possible side effects associated with omega-3 fatty acid supplementation (LOVAZA) include eructation, dyspepsia, taste perversion, constipation, gastrointestinal disorder, vomiting, increased ALT, increased AST, pruritus, rash, hemorrhagic diathesis, urticaria.

#### Vitamin C, 500 mg/day:

The upper limit suggested for daily vitamin C intake is 2,000 mg/day. The daily supplementation provided to patients per this protocol is 500 mg/day, well below the upper threshold.

Possible side effects associated with vitamin C supplementation include diarrhea, nausea, vomiting, heartburn, abdominal cramps, headache, insomnia.

#### L-Arginine, 4.5 grams/day:

There is no recommended daily amount established for arginine supplementation. The observed safe level for oral administration is 9 grams/day and levels used in research vary from 2 to 30 grams/day. The daily supplementation provided to patients per this protocol is 4.5 grams/day, well below the upper threshold.

Possible side effects associated with L-arginine supplementation include abdominal pain, nausea, diarrhea, dyspepsia, palpitations, headache, numbness, bitter taste, and hypotension.

Noted above are the known side effects of the individual supplements. However, this specific combination of supplements has not been studied together in humans and therefore, the risks are unknown.

### **8) Potential Benefits to Subjects**

Patients in either treatment arm may benefit from increased monitoring by research staff with no additional expense to the patient. Research staff will be in constant contact with providers, meaning that providers will be alerted of changes in the patient's medical status potentially sooner than if the patient was not enrolled in the study.

Patients who are randomized to receive the oral immunonutrition supplementation may potentially benefit by receiving a new regimen of medical care for diabetic foot ulcers in addition to standard of care.

Indirectly, patients may benefit by providing new information for medical professionals to better treat similar patients in the future.

### **9) Safety Monitoring Plan**

#### Laboratory Monitoring:

Periodic laboratory and ECG monitoring will be performed to assess safety of the oral supplement as detailed below:

**Lipid panel monitoring:** patients are eligible for study participation if they have had a lipid panel performed within 3 months of study enrollment. An additional lipid panel will be performed at study conclusion (6-week timepoint or within 3 months of study completion) for patients enrolled in the treatment arm.

**Blood glucose monitoring:** blood glucose is routinely monitored in diabetic patients at our institution. This data will be reviewed in the patients' charts as they become available, and the investigators will be alerted to any abnormalities.

**Serum chemistry parameters and hepatic enzymes:** patients are eligible for study participation if they have had a CMP performed within 3 months of study enrollment. An additional CMP will be performed at study conclusion (6-week timepoint or within 3 months of study completion) for patients enrolled in the treatment arm. Patients will have an INR/PT

performed at the time of study enrolled (if not within the past 3 months) to confirm no hepatic impairment.

**Continuous Patient Monitoring:**

Patients enrolled in this study will be flagged in EPIC as a participant in a research study. If a patient presents to an Emergency Department and/or is admitted to a Prisma Health hospital, the study team will be notified via EPIC. The patient's chart will be reviewed to determine the cause of the admission and promptly reported to the study investigators.

**Adverse Event (AE) and Serious Adverse Event (SAE) Reporting:**

Adverse events will be recorded at in-office visits, via study coordinator phone calls, and through manual chart review. All AEs will be reported to the wound care provider, if they are not already aware of the event. Serious adverse events will be immediately reported to all study investigators.

Patients who experience an adverse event (AE) assessed as  $\geq$  Grade 3 (and  $\geq$  Grade 2 for bone marrow and cardiovascular events) per NCI-CTCAE version 5.0^19 will discontinue use of the oral supplement, if in the treatment arm. These subjects will continue to be monitored until the AE resolves or stabilizes. AEs and SAEs will be promptly reported to the IRB and FDA, as required.

**Adverse Event/Outcomes Scheduled Monitoring:**

An independent Data Safety Committee has been assembled for scheduled monitoring of adverse events. The committee is comprised of:

**[name]**

Foot and Ankle Surgeon  
Prisma Health - Upstate  
Steadman Hawkins Clinic of the Carolinas

Following enrollment of 5 subjects to the study (17%), the Data Safety Committee will meet to review data collected to date, including an in-depth review of all recorded AEs and SAEs. The Data Safety Committee will make a determination on the continuation of the study at this point. If the study is allowed to proceed, the Data Safety Committee will continue to meet following the enrollment of each set of 5 patients to repeat this process. If the Data Safety Committee determines that the study should not proceed, all study activities will be

immediately halted. Patients in the treatment arm will be instructed to immediately discontinue the immunonutrition supplements.

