**d. Study Timelines**

We expect this study to be completed within one year of receiving IRB approval. We aim to achieve complete enrollment of 30 participants in a 6- to 9-month period. Following the completion of participant enrollment and data collection, the obtained results will be reviewed and statistically analyzed over a 3-month period. Finally, a manuscript detailing the study results will be written and submitted for publication.

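### Data Safety Committee meetings are triggered only by each 5 enrolments: no stated route brings an SAE to the committee between meetings, no event calls a review, and none follows the meeting tied to the 30th enrolment (low severity, cheap to fix)

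*Combined protocol and SAP*

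**What the plan says.** The committee's rule is in Section 9, Adverse Event/Outcomes Scheduled Monitoring. It first meets once 5 subjects (17%) are enrolled and reviews the data to date, including all AEs and SAEs. Then "The Data Safety Committee will make a determination on the continuation of the study at this point". If the study proceeds, "the Data Safety Committee will continue to meet following the enrollment of each set of 5 patients to repeat this process". A decision not to proceed halts all activity and stops supplements in the treatment arm.

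Individual events follow other routes, also in Section 9:

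- **AE and SAE reporting:** "Serious adverse events will be immediately reported to all study investigators", and "AEs and SAEs will be promptly reported to the IRB and FDA, as required". A treated patient with an AE of Grade 3 or higher (Grade 2 or higher for bone marrow and cardiovascular events) stops the supplement.
- **Continuous Patient Monitoring:** emergency visits and admissions alert the study team, and the chart is "reviewed to determine the cause of the admission and promptly reported to the study investigators".

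Neither route names the committee.

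Two sources of safety data can come in after the meeting tied to the 30th enrolment. One is the treatment-arm safety visit 6-8 weeks after week 6 (Section 6f, item 7). The other is the end-of-treatment CMP and lipid panel, drawn at week 6 or within 3 months of completion (Section 9, Laboratory Monitoring).

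**The concern.** Section 7 says that this combination has not been studied together in humans and that its risks are unknown. If one treated patient has an SAE possibly related to the supplement, the rules in Sections 6k and 9 act on that patient. Whether other patients should continue to be randomised and dosed is a study-level question, and the committee is the one independent body that the protocol gives stated power to answer it by halting the study. Under the rule as written, the committee need not hear of the event until the next set of 5 is complete. There is no calendar backstop, so slower accrual lengthens the wait.

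The same gap recurs at the end. If the sixth meeting is held promptly after the 30th enrolment, some treated patients are still dosing, and nothing requires a later event to reach the committee. Once dosing has ended, the loss is in the completeness of the committee's picture and not in protection. Late AEs and the last patients' liver tests would not come before the committee, although Section 7 lists "increased ALT, increased AST" among possible effects of the omega-3 product.

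**Working it through.** **The plan's own figure.** 5/30 = 16.7%, which rounds to the stated 17%. Reviews fall at 5, 10, 15, 20, 25 and 30 enrolled: 30/5 = 6 meetings.

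**Inputs from the protocol.** 30 patients, 15 per arm (Section 6c); 6 weeks of supplement (Section 6f); accrual as in Section 6d: "We aim to achieve complete enrollment of 30 participants in a 6- to 9-month period". Planned exposure is 15 × 6 = 90 supplement patient-weeks.

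**Assumptions.** Even accrual over T = 26 or 39 weeks, even 1:1 allocation, full dosing, and each meeting held on the day its set of 5 is complete. The protocol gives none of these except the 6-9 months and the equal arms.

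**Spacing.** L = T/6 = 4.3 weeks (T = 26) or 6.5 weeks (T = 39). At the slower pace the interval exceeds the 6-week course.

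**Steady state.** Treated enrolments per week = 15/T = 0.577 or 0.385. Patients on supplement at once = 6 × 15/T = 3.46 or 2.31.

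| For an event in a steady interval | T = 26 | T = 39 |
|---|---|---|
| Mean wait, L/2 (weeks) | 2.2 | 3.3 |
| Mean patient-weeks before next meeting | 3.46 × 2.17 = 7.5 | 2.31 × 3.25 = 7.5 |
| Mean treated enrolments before next meeting | 0.577 × 2.17 = 1.25 | 0.385 × 3.25 = 1.25 |
| Worst case (event just after a meeting) | 15 and 2.5 | 15 and 2.5 |

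**With a review within 7 days, or the next meeting if sooner.** An event falls in the last week of an interval with probability 1/L and then waits half a week on average; otherwise it waits 1 week. Mean wait = 1 − 1/(2L) = 0.88 (T = 26) or 0.92 (T = 39) weeks.

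- Patient-weeks: 3.46 × 0.88 = 3.1 or 2.31 × 0.92 = 2.1. Mean saving: 7.5 − 3.1 = 4.4 or 7.5 − 2.1 = 5.4.
- Treated enrolments: 0.577 × 0.88 = 0.51 or 0.385 × 0.92 = 0.36. Mean saving: 1.25 − 0.51 = 0.7 or 1.25 − 0.36 = 0.9.

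**First interval.** Few patients are on supplement yet, so it holds less in total: (15/26) × 4.33²/2 = 5.4 patient-weeks at T = 26, and (15/39) × (6²/2 + 6 × 0.5) = 8.1 at T = 39.

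**After the sixth meeting.**

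| Sixth meeting held | Formula | Patient-weeks left (T = 39 to T = 26) | Share of 90 |
|---|---|---|---|
| Same day as 30th enrolment | (15/T) × 6²/2 | 6.9-10.4 | 8-12% |
| 2 weeks later | (15/T) × 4²/2 | 3.1-4.6 | 3-5% |
| 6 weeks later | none left | 0 | 0% |

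**Reconciliation.** At T = 39: 8.1 + 5 × 15 + 6.9 = 90. At T = 26 the second interval is still partly ramping up and holds (15/26) × [(6² − 4.33²)/2 + 6 × (8.67 − 6)] = 14.2, so 5.4 + 14.2 + 4 × 15 + 10.4 = 90.

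**Data outstanding at a same-day sixth meeting (completeness only).** Safety visit pending: 15 × 12/39 = 4.6 to 15 × 14/26 = 8.1 of 15 treated patients. End-of-treatment CMP pending: 15 × 6/39 = 2.3 to 15 × 6/26 = 3.5 if drawn at week 6. If it is drawn 13 weeks after the patient's week 6, the figures are 15 × 19/39 = 7.3 to 15 × 19/26 = 11.0.

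**The case against.** Six independent reviews for a 30-patient, single-centre, open-label pilot are already dense oversight. The committee was set up for scheduled monitoring, and single events were deliberately given to others: immediate SAE reports to investigators, IRB and FDA reports as required, individual stopping by grade, provider withdrawal (Section 6k) and daily chart review of the supplement arm (Section 9, surgery plan). Section 7 puts each dose below a stated limit: 1.68 g against 3.0 g/day EPA + DHA, 500 mg against 2,000 mg vitamin C, and 4.5 g against 9 g arginine. Nothing forbids an unscheduled meeting. All of this stands, and it is why the point is minor. What remains is that frequent meetings set by enrolment give no response to an event, and the committee cannot call a meeting about an event that nobody is told to send it.

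A reader might infer four stronger things that the documents do not support:

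- **That SAEs escape outside review, or that the committee may not meet between sets.** The IRB and FDA receive reports as required, and the protocol is silent on unscheduled meetings; it does not bar them.
- **That 15 patient-weeks are typically at stake.** That is the worst case in a steady interval. The mean is half of it, and the whole first interval, when the combination is first given, holds only 5.4-8.1.
- **That 8-12% of exposure must fall after the last meeting.** This assumes a same-day meeting. The protocol sets no lag, and a meeting 6 weeks later leaves none.
- **That late events go unreviewed.** The provider records AEs at the safety visit and orders the final labs, and the IRB and FDA are told as required. Only committee review is missing.

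**Conclusion.** The point holds as a low-severity gap in committee oversight, not as a failure of safety monitoring. The text sets meetings by enrolment only, gives no route for SAEs to the committee between meetings, names no event that calls a review, and schedules nothing after the meeting tied to the 30th enrolment. A 7-day review would on average save about 4.4-5.4 supplement patient-weeks and less than one treated enrolment per qualifying event in a steady interval. The preventable exposure after the sixth meeting ranges from 0 to 10.4 of 90 patient-weeks, depending on accrual and on when that meeting is held.

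These sizes rest on assumed even accrual, full dosing and, except where a lag is stated, same-day meetings. The text between the opening of the committee's member list and its meeting rule was not available in the copy read here. It probably lists members only, but a further meeting rule there cannot be fully excluded.

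**What to change.** In Section 9, under AE and SAE Reporting and under Scheduled Monitoring, keep the six meetings and add:

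1. Every SAE in either arm, and every treatment-arm event that meets the existing threshold for stopping the supplement, is forwarded to the existing committee when it is reported, until the last treated patient's safety visit.
2. A treatment-arm SAE that the provider judges possibly related to the supplement calls an unscheduled committee review, for example within 7 days. The committee decides whether to pause randomisation or dosing. There is no automatic hold, and non-serious threshold events are forwarded without calling a review.
3. Optional, for completeness of committee review only: one close-out review by circulated summary after the last safety visit and the last end-of-treatment CMP and lipid results.

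**Cost.** Protocol wording and a few calls. If 0-20% of treated patients had an SAE judged possibly related (an assumed range; the documents give no rate), 15 patients give 15 × 0 = 0 to 15 × 0.20 = 3 unscheduled reviews. The provider's judgement of relatedness and the daily chart review already exist. The downsides are a possible brief enrolment pause and, if item 3 is adopted, a close-out as late as 6 + 13 = 19 weeks after the 30th enrolment when the last labs are drawn at the 3-month limit.

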7. A follow-up safety visit will be conducted by the provider for patients randomized to the treatment group 6-8 weeks after the week 6 office visit. This visit is more than 5 half-lives after supplementation discontinuation and will allow for capture of adverse events that may occur after completion of dosing. The wound will be visualized during this visit. Adverse events and wound details will be documented in the patient's chart. This visit will be conducted in-office if the patient is already scheduled to see their provider within the visit window. If the patient is not scheduled to see their provider, this visit may be conducted virtually through EPIC.
8. Patient charts will be monitored throughout the patient's participation in the study for any signs of infection, unscheduled visits, calls to the provider, and/or onset of severe adverse events. Patient charts will continue to be monitored for one year following the completion of the study to assess ulcer recurrence rates.

The schedule of events is outlined below and is pictured in Appendix 1:

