#### **Final Safety Follow-up Visit**

6-8 Weeks after Office Visit 3/discontinuation of supplement

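### The committee stop rule halts every study activity and makes no exception for safety follow-up of patients already dosed

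*Combined protocol and SAP*

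**What the plan says.** **The stop rule.** Section 9, Adverse Event/Outcomes Scheduled Monitoring, sets a committee review at 5 enrolled subjects and after each further 5. The rule for a negative decision opens: "If the Data Safety Committee determines that the study should not proceed, all study activities will be". It makes the stop take effect at once and then turns to dosing: "immediately halted. Patients in the treatment arm will be instructed to immediately discontinue the immunonutrition supplements". The only instruction about treated patients is to stop taking the supplements.

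**The safety follow-up planned for a patient who runs the full course.**

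- Section 9, AE and SAE Reporting: "Adverse events will be recorded at in-office visits, via study coordinator phone calls, and through manual chart review".
- Section 6.f, step 8: charts are watched throughout participation "in the study for any signs of infection, unscheduled visits, calls to the provider, and/or onset of severe adverse events".
- Section 9, Laboratory Monitoring, treatment arm only: "An additional CMP will be performed at study conclusion (6-week timepoint or within 3 months of study completion". The lipid panel has the same timing.
- Section 6.f, step 7, treatment arm only: a safety visit 6-8 weeks after the week 6 visit, which "will allow for capture of adverse events that may occur after completion of dosing". Appendix 1 times it as "6-8 Weeks after Office Visit 3/discontinuation of supplement".

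**Text that gives some cover after a stop.**

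- Section 9, AE and SAE Reporting, keeps monitoring any patient with an adverse event of Grade 3 or above (Grade 2 or above for bone marrow and cardiovascular events) until it resolves or stabilises.
- Section 9, Continuous Patient Monitoring: "If a patient presents to an Emergency Department and/or is admitted to a Prisma Health hospital, the study team will be notified via EPIC".
- Section 9's plan for unplanned surgery places a flag in EPIC telling surgeons to contact the PI.
- Section 12 describes the two-weekly wound visits as standard care.

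**The concern.** The committee's reviews centre on adverse events, so a stop would most likely follow a safety concern. Section 7 says this combination has not been studied together in humans and that its risks are unknown. Section 6.f schedules a late visit precisely to catch events after dosing. A halt on everything, followed as written, ends planned safety data collection in recently dosed patients just when those data would help describe the problem that caused the stop.

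The laboratory draw shows this most clearly. Section 7 lists raised ALT and AST as possible effects of the omega-3 product, and these need a blood test to detect. The treated arm has one protocol-scheduled CMP after baseline, at week 6 or within 3 months of completion. An early stop could remove it for every treated patient.

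**Working it through.** **1. The plan's own figure.** 5/30 = 16.7%, which rounds to the stated 17%. It reproduces.

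**2. Does the halt reach follow-up, or only enrolment and dosing?** Three features of the text point to follow-up.

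- Section 6.f, step 2, uses the term study activities for procedures done on an individual patient, who takes them up again at the next visit once laboratory or ECG results are in.
- The stop rule deals with dosing in a separate sentence, so the halt must cover something more.
- At the sixth review all 30 patients are enrolled. Beyond dosing, what is left to halt is mainly visits, calls, labs and chart review.

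**3. Does other text override the halt?**

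| Provision | What it keeps | What it leaves open |
|---|---|---|
| Monitoring of qualifying AEs (Section 9) | Known higher-grade events | Lower-grade or undetected events |
| EPIC alert (Section 9) | Emergency visits, admissions to the sponsor's hospitals | Anything short of these |
| EPIC surgery flag (Section 9) | Surgical risk | Other events |
| Routine wound visits (Section 12) | Clinical contact, some AE recording | Coordinator calls, study chart review, labs, safety visit |
| Appendix 1 visit timing | Could fit an early stop | Not linked to a committee halt |
| Laboratory timing (Section 9) | Could be read as due at an early stop | Its parenthesis points to the patient's own week 6 or completion |

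None of them says that follow-up survives a committee stop.

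**4. How many treated patients are exposed?** Inputs: 30 patients, 15 per arm (Section 6.c); enrolment in 6-9 months (Section 6.d); 6 weeks of dosing; safety visit 6-8 weeks later, so at week 12-14. Assumptions: even accrual; expected treated share one half; the patient enrolled at the review itself not counted, because dosing starts the day after supply (Appendix 6).

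Spacing is 26/30 = 0.867 weeks (6 months) or 39/30 = 1.3 weeks (9 months). The patient enrolled j places before the review has been in the study j × spacing weeks.

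- Still dosing (under 6 weeks), 6-month accrual: 6 × 0.867 = 5.2 and 7 × 0.867 = 6.07, so 6 patients, but only 4 exist at review 1. With 9-month accrual: 4 × 1.3 = 5.2 and 5 × 1.3 = 6.5, so 4 patients.
- Off dosing, before the safety visit (6 to under 12 or 14 weeks), 6-month accrual: 0 at review 1, 3 at review 2, 7-8 at review 3, 7-10 at reviews 4-6. With 9-month accrual: 0, 5, 5-6 and 5-6.

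Halving for the treated arm:

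| Review | Still dosing (labs and visit outstanding) | Off dosing (visit outstanding, labs perhaps done) | Total treated |
|---|---|---|---|
| 1 | 2 | 0 | 2 |
| 2 | 2-3 | 1.5-2.5 | 4.5 |
| 3 | 2-3 | 2.5-4 | 4.5-7 |
| 4-6 | 2-3 | 2.5-5 | 4.5-8 |

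The columns do not add end to end, because faster accrual raises one group and can lower the other. Counting the patient enrolled at the review adds 0.5 to the first group and to each total.

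Cross-check in continuous form, min(number enrolled, rate × window)/2: the lowest later value is (30/39) × 12/2 = 4.6 and the highest is (30/26) × 14/2 = 8.1. These agree.

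**5. Labs at the first review.** The earliest patient is 4 × 0.867 = 3.5 to 4 × 1.3 = 5.2 weeks in. On these assumptions nobody has reached the week 6 draw.

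**The case against.** The strongest reply is that the sentence means stopping the conduct of the trial, while the more specific safety provisions of the same section continue. Those provisions are not made conditional on the trial going on, and Appendix 1's discontinuation trigger fits a patient told to stop early. That may well be what the drafters intended. It remains an inference, though: the halt is unqualified, and none of these provisions refers to it.

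The reply does succeed in limiting the size of the point. The patients most likely to matter in a safety stop, those with qualifying events, stay under monitoring. Routine office visits are themselves a listed source of adverse events, and the safety visit may be virtual. The end-of-dosing labs and that visit are in the treated arm only, so they offer no comparison between arms, and the baseline labs may be up to 3 months old.

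A reader might infer that a stop would leave treated patients without any safety oversight. The documents do not support that, given the partial cover set out above. Nor should the daily chart review of the supplement arm be counted as lost general surveillance: it is described as serving communication about surgery. Finally, nothing shows that the sponsor intends to abandon follow-up or that staff would read the sentence literally.

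**Conclusion.** The point holds as a modest, conditional safety gap in the wording of the stop rule. Two things must happen before it does harm: a committee stop, whose probability the documents do not give, and literal application of the sentence. What would then go uncovered is the scheduled capture of lower-grade or not yet detected events, one CMP and lipid draw, and one safety visit. The group concerned is an expected 2 to 8 treated patients, depending on the review and the accrual rate, less any kept under monitoring for a qualifying event. The counts rest on even accrual and 1:1 allocation; they size the group and say nothing about how likely the loss is. The point should be corrected because an unqualified stop instruction ought not to depend on staff guessing its exceptions.

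**What to change.** In Section 9, Adverse Event/Outcomes Scheduled Monitoring, replace the halt on all activities with a halt on screening, enrolment, randomisation and dosing. Keep the instruction to stop the supplements. Then add that planned safety follow-up continues, as follows:

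- Open adverse events in either arm are followed until they resolve or stabilise, as the AE and SAE Reporting text already provides for qualifying grades.
- For treated patients, adverse-event collection continues up to and including a safety visit 6-8 weeks after the last dose, in line with the timing in Appendix 1.
- Treated patients have the planned CMP and lipid panel if not yet done.

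The cost is one or two sentences in an amendment and a small amount of continued follow-up work, all of it already planned. Section 12 already pays for the treated arm's labs and for the safety visit when it is an extra one. The safety visit gives collection in treated patients a defined end, and controls acquire no open-ended calls and no new procedures.
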